10.3. Secondary Efficacy Endpoints and Analysis

Secondary efficacy endpoints during Initial Period:

Secondary endpoints during Initial Period will be analyzed for both populations (Full population; Baseline PP NRS ≥ 7) on the ITT population.

[figure not shown]
CCI

Binary endpoints will be analyzed using a Cochran-Mantel-Haenszel test adjusted for the randomized stratification variables (IGA severity [3=moderate, 4=severe] and PP NRS ≥ 7 , < 7] for full population; IGA severity only for Baseline PP NRS ≥ 7 population). Any subjects with missing data at respective Weeks will be regarded as a non-responder.

CCI

This document is confidential.

CCI

[figure not shown]
1.0

CD14152.SPR118161.SAP.V01

Approved 10-Nov-2022 00:00:00

This document is confidential.

CCI

[figure not shown]
1.0

CD14152.SPR118161.SAP.V01

Approved 10-Nov-2022 00:00:00

This document is confidential.

CCI

[figure not shown]
1.0

CD14152.SPR118161.SAP.V01

Approved 10-Nov-2022 00:00:00

This document is confidential.

CCI

1.0

CD14152.SPR118161.SAP.V01

Approved 10-Nov-2022 00:00:00

This document is confidential.

CCI

10.3.3. Pruritus Numeric Rating Scale (NRS)

The Pruritus NRS is a scale to be used by the subjects to report the intensity of their pruritus (itch) during the last 24 hours. Peak pruritus (PP NRS) is an assessment of the maximum itch intensity in that Period while average pruritus (AP NRS) provides a measure of overall pruritus intensity.

Subjects will be asked the following question:

- For maximum itch intensity (PP NRS): “On a scale of 0 to 10, with 0 being ‘no itch’ and 10 being the ‘worst itch imaginable’, how would you rate your itch at the worst moment during the previous 24 hours?”
- For average itch intensity (AP NRS): “On a scale of 0 to 10, with 0 being ‘no itch’ and 10 being the ‘worst itch imaginable’, how would you rate your itch overall during the previous 24 hours?”

The screening PP/AP NRS will be determined by a single assessment using the PP/AP NRS (score ranging from 0 to 10) for the 24-hour Period immediately preceding the screening visit. The Baseline PP/AP NRS will be determined based on the average of daily PP/AP NRS (score ranging from 0 to 10) respectively during the 7 days immediately preceding Baseline (rounding to nearest whole number is not permitted). A minimum of 4 daily scores out of the 7 days immediately preceding Baseline is required for this calculation. PP/AP NRS at all follow-up visits will be determined in the same manner. Refer the details for the analysis visit window for diary data in Section 8.4. Subjects will receive instructions on how to record their PP/AP NRS scores and will complete the assessment once daily in the evening throughout the clinical study (including the run-in and the Follow-up Period).

In case of diary data, if the date of rescue therapy use is within the analysis visit window, the subject at the analysis visit will be treated as treatment failure except for OC analysis and the weekly average will be imputed using the worst-case value for analysis.

During Initial Period:

PP NRS will determined by an average as described above at every week from Baseline to Week 16 as a continuous variable for the Initial Period.

Descriptive summary of PP NRS will be provided for ITT and PP populations. Absolute change and percent change from Baseline for the PP NRS score will also be included in the summary.

AP NRS will determined by an average as described above at every week from Baseline to Week 16 as a continuous variable of the Initial Period. Descriptive summary of AP NRS will be provided for ITT population. Absolute change and percent change from Baseline for the AP NRS score will also be included in the summary.

Change from Baseline in PP NRS at each analysis visit up to Week 16 will be analyzed using ANCOVA, with missing values imputed using MI under MAR assumption, and MMRM. For the MI and MMRM analyses the least squares means (LSMeans), standard error of LSMean, and 95% CI for change from Baseline, as well as the difference in LSMean between the treatment groups, the two-sided 95% CI, and associated p-value will be presented. In addition, percent change from Baseline in PP NRS at each analysis visit up to Week 16 will be analyzed using MMRM.

Change from Baseline in percentage of itch-free days based on PP/AP NRS (score of 0 or 1) will also be summarized descriptively by visit.

This document is confidential.

Improvement in PP/AP NRS will be calculated using Baseline as the reference point for change in PP/AP NRS score. The proportion of subjects with PP NRS improvement ≥ 4 will be presented using OC, non-responder and LOCF. The proportion of subjects with an improvement of PP NRS ≥ 4 at Week 8 and Week 12, the proportion of subjects with a PP NRS < 2 at Week 1, Week 2, Week 8 and Week 12, the proportion of subjects with AP NRS ≥ 4 at each visit up to Week 16, and the proportion of subjects with AP NRS < 2 at each analysis visit up to Week 16 will be analyzed using non-responder imputation. The estimate of treatment unadjusted and strata-adjusted differences with the corresponding 2-sided 95% confidence intervals, and p-values from the Cochran-Mantel-Haenszel test will be presented.

Line plot for proportion of subjects with PP NRS improvement ≥ 4 and for proportion of subjects with PP NRS < 2 using Non-responder imputation will be presented for Initial Period on the ITT population.

"Itch-free days" will be defined if PP/AP NRS score is 0 or 1. The proportion of "itch-free days" will be calculated using 7 days diary data for the visit. A minimum of 4 daily scores out of the 7 days for the visit is required for the proportion calculation. The proportion of "itch-free days" will be calculated using number of days of PP/AP NRS score of 0 or 1 divided by number of days reported during the week. The summary of proportion of "itch-free days" based on PP NRS/AP NRS will be presented for Initial Period.

[figure not shown]
During Maintenance Period:

PP/AP NRS will be determined by an average using 7 days data before the visit for Week 24, Week 32, Week 40, Week, Week 48 as a continuous variable for the Maintenance Period. Absolute change and percent change from Baseline and Maintenance Baseline (Week 16) for the PP/AP NRS score will also be included in the summary. No hypothesis testing will be performed.

Improvement in PP/AP NRS will be calculated using Baseline and Maintenance Baseline (Week 16) as the reference point for change in PP/AP NRS score. The proportion of subjects with an improvement of PP/AP NRS ≥ 4 and the proportion of subjects with a PP/AP NRS < 2 will be summarized.

[figure not shown]
For the subset of patients achieving an improvement of PP/AP NRS ≥ 4 at Week 16, the proportion of subjects achieved such an improvement at each analysis visit during the Maintenance Period will be summarized. For the subset of patients achieving a PP/AP NRS < 2 at Week 16, the proportion of subjects with PP/AP NRS < 2 at each visit during the Maintenance Period will be summarized using OC.

Line plot for proportion of subjects with PP NRS improvement ≥ 4 and for proportion of subjects with PP NRS < 2 using Non-responder imputation will be presented for Maintenance Period on the ITT population.

This document is confidential.

CCI

[figure not shown]
1.0

CD14152.SPR118161.SAP.V01

Approved 10-Nov-2022 00:00:00

This document is confidential.

CCI

[figure not shown]
1.0

CD14152.SPR118161.SAP.V01

Approved 10-Nov-2022 00:00:00

This document is confidential.

CCI

1.0

CD14152.SPR118161.SAP.V01

[figure not shown]
Approved 10-Nov-2022 00:00:00

This document is confidential.

[figure not shown]
1.0

CD14152.SPR118161.SAP.V01

Approved 10-Nov-2022 00:00:00

CCI

[figure not shown]
1.0

CD14152.SPR118161.SAP.V01

Approved 10-Nov-2022 00:00:00

This document is confidential.

CCI

[figure not shown]
1.0

CD14152.SPR118161.SAP.V01

Approved 10-Nov-2022 00:00:00

This document is confidential.

CCI

[figure not shown]
1.0

CD14152.SPR118161.SAP.V01

Approved 10-Nov-2022 00:00:00

This document is confidential.

CCI

[figure not shown]
1.0

CD14152.SPR118161.SAP.V01

Approved 10-Nov-2022 00:00:00

This document is confidential.

CCI

[figure not shown]
1.0

CD14152.SPR118161.SAP.V01

Approved 10-Nov-2022 00:00:00

This document is confidential.

CCI

1.0

CD14152.SPR118161.SAP.V01

[figure not shown]
Approved 10-Nov-2022 00:00:00

This document is confidential.

1.0

CD14152.SPR118161.SAP.V01

Approved 10-Nov-2022 00:00:00

CCI

This document is confidential.

11. Pharmacokinetics

The serum concentration of nemolizumab will be assessed at Baseline, Week 4, Week 8, Week 12 and Week 16 during the Initial Period and at Week 20, Week 24, Week 32, Week 40, and Week 48 during the Maintenance Period and Follow-up visit. PK analyses are required during any unscheduled visit conducted for safety reasons. As a guideline, PK samples should be collected at approximately the same time of day throughout the study, to the extent possible, before study drug injection (pre-dose samples).

11.1. Pharmacokinetic Concentration Presentation

Serum concentration data (unit: ng/mL) will be summarized on the PK analysis population by visit from Baseline to Week 16 for the Initial Period and from Week 16 to Week 48 for the Maintenance Period, using the following statistics: arithmetic mean, standard deviation, coefficient of variation (CV), geometric mean, geometric CV, median, minimum, maximum, 95% CI, and number below the limit of quantification (BLQ).

Mean serum concentration will be plotted by visit for Initial Period and Maintenance Period on both a linear and semi-logarithmic scale on the PK analysis population.

Individual serum concentrations will be listed on the PK analysis population.

11.2. Pharmacokinetic Parameters Estimation

Pharmacokinetic parameters may be calculated, if needed, by a designated CRO using 2 analyses:

- PK parameters may be derived, if needed, using a non-linear mixed effect modeling approach with NONMEM. A pre-specified population PK model based on existing information from previous studies in adults and adolescents (first-order absorption and a 1-compartment distribution model) will be updated with the nemolizumab serum concentrations obtained in this study.
- In addition, a static analysis based on serum concentration may be performed, if needed, using a noncompartmental analysis, for each subject based on concentration before dosing, to obtain areas under the curve. Data from subjects with missing concentration values (missing samples) may be used if PK parameters can be estimated using the remaining data points.

If the population PK and/or noncompartmental analyses will be performed, details will be specified in an ad hoc PK Analysis Plan. Results of population PK and/or noncompartmental analyses will not be included in the CSR final TFLs but in a dedicated PK Analysis Report separately.

This document is confidential.

12. Pharmacodynamics

Blood and stratum corneum (D-Squames) samples will be collected at selected sites to investigate the effect of nemolizumab (CD14152) on RNA and protein biomarkers, including but not limited to TARC, IgE, and IL-31. The recruitment of subjects for this part of the study will continue until the end of recruitment period of the study. The analysis will be performed by the designated CRO.

1.0

CD14152.SPR118161.SAP.V01

Approved 10-Nov-2022 00:00:00

This document is confidential.

13. Safety

All safety data will be summarized and listed on the Safety population.

Safety assessments will be conducted for all subjects at the screening visit (upon signing of the ICF) and at every subsequent visit. Safety will be assessed on the basis of AEs, unexpected adverse reactions, clinical laboratory data, vital signs, physical examination, respiratory examination, and ECG parameters. Summary of all safety endpoints will be presented by study Period (Initial Period, Maintenance Period, and Follow-up Period) for each treatment group.

13.1. Adverse Events

Adverse events (AEs) will be coded using MedDRA Version 25.0, March 2022.

Treatment-emergent AEs, defined as those AEs occurring after the first administration of study treatment until end of study, will be tabulated in frequency tables by System Organ Class (SOC) and Preferred Term (PT) based on the Medical Dictionary for Regulatory Activities for each study period (Initial Period, Maintenance Period, and Follow-up Period). Missing date information will be handled using the algorithm described in Section 8.3.

Additional summary tables by SOC and PT will be provided for SAEs, AEs related to the study drug(s), AEs related to the study procedure, adverse events of special interest (AESIs), and AEs leading to treatment discontinuation and study withdrawal.

AEs will be summarized using the number and percent of subjects reporting each SOC and PT and sorted alphabetically by SOC and by descending frequency of PT within SOC.

Subjects who experienced multiple events within the same SOC will be counted once in the SOC summary. When summarizing by causality or maximum severity, if a subject experiences more than 1 occurrence of the same AE, the occurrence with the greatest severity and the closest association with the study drug will be used in summary tables. For summary by maximum severity, subjects who experience multiple occurrence of an AE, the most severe category for each SOC and for each PT within each SOC will be considered in the summary.

TEAEs related to study drug/study procedure are those that are identified as reasonable possibility.

If relationship or severity is missing, the event will be considered as AE related to study drug/study procedure or severe AE.

An AESI is a noteworthy treatment-emergent event for the study drug that should be monitored closely and reported promptly. An AESI can be either serious or non-serious. Based on the potential risks of nemolizumab and the risks associated with biologics in general (i.e., class effects), the following AEs will be considered as AESIs: Injection-related reactions, Newly diagnosed asthma or worsening of asthma, Infections, Peripheral edema:limbs, bilateral, Facial edema and elevated ALT or AST (>3xULN) in combination with elevated Bilirubin (>2xULN).

The following summary tables for TEAEs will be presented for all TEAEs (i.e., TEAE, all causalities) and study drug related TEAEs separately and by period (treatment period which includes Initial Period and Maintenance Period) and Follow-up Period.

- Overall Summary of TEAEs
Overall summary table includes summary of subjects reporting TEAEs, TEAE related to study drug, TEAE related to protocol procedure (including topical background therapy), Serious TEAE, Serious TEAE related to study drug, Severe TEAE, TEAE leading to temporary discontinuation of

This document is confidential.

study drug, TEAE leading to permanent discontinuation of study drug, TEAE leading to permanent discontinuation from study, TEAE of special interest, TEAE leading to death, TEAE related to study drug leading to death. For the summary of Follow-up period, the summaries of 'temporary discontinuation of drug' and 'permanent discontinuation of drug' will not be provided.

- TEAEs by System Organ Class and Preferred Term
- Serious TEAEs by System Organ Class and Preferred Term
- TEAEs by System Organ Class, Preferred Term and Maximum Severity
- Severe TEAEs by System Organ Class and Preferred Term
- TEAEs Leading to Permanent Discontinuation of Study Drug by System Organ Class and Preferred Term, which is only for Treatment period. No summary of Follow-up period.
- TEAEs occurred in $\geq 5\%$ of subjects by System Organ Class and Preferred Term
- TEAEs occurred in $\geq 5\%$ of subjects by Preferred Term

For overall study period which includes all periods (initial, maintenance and follow-up), the following summary tables will also be presented and repeated for all TEAEs (all causalities) and study drug related TEAEs.

- Overall Summary of TEAEs
- TEAEs by System Organ Class and Preferred Term

The overall study period summary will be presented by 4 treatment groups (Nemolizumab 30mg Q4W, Nemolizumab 30mg Q4W to Q8W, Nemolizumab 30mg Q4W to Placebo, and Placebo). Nemolizumab 30mg Q4W includes all subjects in the population who received Nemolizumab 30mg in Initial Period or who received Nemolizumab 30mg Q4W continuously during Initial and Maintenance Periods. Similarly, Placebo includes all subjects in the population who received Placebo in Initial Period or who received Placebo continuously during Initial and Maintenance Periods.

For the subset of subjects with COVID-19 infection, the following summary tables will be provided additionally and it will be repeated for all TEAEs and Study drug related TEAEs, separately.

- Overall summary of TEAEs
- TEAEs by System Organ Class and Preferred Term
- Serious TEAEs by System Organ Class and Preferred Term
- TEAEs of Special Interest by Category, System Organ Class and Preferred Term

A separate summary below for TEAEs of Special Interest will be provided by periods (initial, maintenance) and repeated for all TEAEs (all causalities) and Study drug related TEAEs.

- Overall Summary of TEAEs of Special Interest
- TEAEs of Special Interest by Category, System Organ Class and Preferred Term
- TEAEs of Special Interest by Category, System Organ Class, Preferred Term and Maximum Severity

Adjudicated events will also be summarized as below by periods (initial, maintenance) and repeated for all TEAEs (all causalities) and Study drug related TEAEs.

This document is confidential.

- Adjudicated TEAEs by System Organ Class and Preferred Term, which are confirmed by Independent Adjudication Committee (IAC).
- Confirmed Adjudicated TEAEs by System Organ Class, Preferred Term and Maximum Severity. Maximum severity will be based on the severity adjudicated by IAC.
- Asthma TEAEs and TEAE of Special Interest reported by Investigator with Adjudication by IAC, which include the data reported by Investigator and adjudications by IAC.

The subgroup summary by country and age group will also be provided for the following summaries. It will be repeated for all TEAEs and Study drug related TEAEs and for Treatment period, Follow-up period and Overall period, separately.

- Overall summary of TEAEs
- TEAEs by System Organ Class and Preferred Term

In addition, the exposure-adjusted incidence rate (i.e., number of subjects per 100 patient-years) will be summarized for all TEAEs (all causalities) and study drug related TEAEs during Treatment Period.

Exposure-adjusted incidence rates of TEAEs is defined as the number of subjects exposed to treatment and experiencing a certain event divided by the total time of all subjects who are at risk for the event. Specially, for subjects with no event the exposure time is the time from the first drug intake to the end of treatment period. Exposure years is calculated as last study drug exposure date minus first study drug exposure date plus one, divided by 365.25 which is the number of days count in a year. This exposure year calculated for each subject is then added cumulatively and is derived for each treatment arm. So each treatment arm will have one value for exposure years (aka. patient years). The exposure year calculation is different in case of subjects who have completed the study or discontinued from the study or having withdrawn from the study due to any reason. Only the event occurred during the treatment period will account for calculation.

Subject listings will be presented for all TEAEs, TEAEs of special interest, serious TEAEs, severe TEAEs, TEAE leading to permanent discontinuation of study drug, TEAEs leading to death and pre-treatment AEs. Subject listings of TEAEs for subjects with COVID-19 infection and adjudicated Asthma TEAEs will also be listed.

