Based on the phase 2b results (Protocol 114322), it is estimated that 15% of subjects will drop out from the initial treatment period. Assuming a 45% responder rate with active treatment and 12% with placebo, approximately 216 subjects will participate in the maintenance period (190 nemolizumab and 26 placebo subjects).

Table 5: Maintenance Period Re-Randomized Group Assignments

Group	Treatment	Dose	Week(s)	Route	Schedule
1A	Nemolizumab (CD14152)	30 mg	16, 20, 24, 28, 32, 36, 40, 44	sc	Q4W
1B	Nemolizumab (CD14152)	30 mg	16, 20*, 24, 28*, 32, 36*, 40, 44*	sc	Q8W*
1C	Placebo	Placebo	16, 20, 24, 28, 32, 36, 40, 44	sc	Q4W

**with placebo Q4W at Week 20, 28, 36, and 44 to maintain blind*

Abbreviation(s): Q4W=every 4 weeks; Q8W=every 8 weeks; sc=subcutaneous.

CONFIDENTIAL

Beginning at Week 16, subjects in group 1A will receive active (ie, nemolizumab [CD14152]) study drug injections Q4W up to Week 44. Subjects in group 1B will receive active (ie, nemolizumab [CD14152]) study drug injections Q8W, with placebo at alternating visits to maintain the blind. Group 1B subjects will receive the last active study drug injection at Week 40 (final injection at Week 44 will be placebo). Group 1C subjects will receive placebo Q4W (ie, through Week 44).

Clinical assessments will occur according to the schedule of assessments through the Week 48 visit (see Section 8.1.2). Subjects should continue the same background topical therapy used in the initial treatment period leading up to the Week 16 visit, including tapering or complete cessation (no use), if applicable. Throughout the maintenance period, adjustments to background topical therapy, as determined by the investigator, are permitted based on the subject's clinical response.

Primary maintenance effect will be evaluated based on Week 48 assessments. All maintenance endpoints will be analyzed independently from each pivotal study and by using pooled data after the completion of both trials.

Subjects requiring rescue before the Week 32 must undergo a required wait period (with continued study visits) until Week 32, at which time they may be considered for LTE eligibility/participation. Thereafter, no wait period is required. See Section 8.5.1 for details.

Subjects who complete the Week 48 visit may be eligible to enroll into the LTE study (Protocol 118163). The follow-up visit is not required for subjects who participate in the LTE study.

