4.1. Brief Description

This is a randomized, double-blind, placebo-controlled, multicenter, parallel-group study in adult and adolescent subjects with moderate-to-severe AD. Eligible subjects must have a documented history of inadequate response to topical AD medication(s).

Approximately 750 total subjects will be randomized (2:1) to receive either nemolizumab (CD14152) or placebo, stratified by Baseline disease severity (Investigator's Global Assessment [IGA]; moderate: IGA = 3; severe: IGA = 4) and peak pruritus numeric rating scale (PP NRS) severity (PP NRS \geq 7; PP NRS < 7). A minimum of 250 subjects will be randomized in each PP NRS strata. Clinical responders at Week 16 who were treated by Nemolizumab during Initial Period (i.e., the end of Initial treatment/beginning of Maintenance) will be re-randomized (1:1:1) to different treatment regimens (injections every 4 weeks [Q4W] or every 8 weeks [Q8W] of nemolizumab [CD14152] or placebo Q4W). All placebo-treated subjects (i.e., subjects in placebo from the Initial Period) who responded to placebo during the Initial Period will continue to receive placebo Q4W in the Maintenance Period.

The study consists of 4 Periods over approximately 60 weeks: Screening (including run-in), Initial, Maintenance, and Follow-up (unless the subject is a non-responder at Week 16, at which their participation could last up to 28 weeks).

Screening Period:

The Screening Period (approximately 2-4 weeks before planned Day 1/Baseline) will evaluate subject eligibility and introduce standardized background topical therapy over a Run-in Period of at least 2 weeks (i.e., 14 days) before Day 1/Baseline. Subjects may be rescreened once unless the reason for screen failure is related to disease severity inclusion criteria (IGA, EASI, BSA, and PP NRS). The latter subjects are not permitted to rescreen.

Initial Period:

The Initial Period is defined as Day 1/Baseline through Week 16 (before the Week 16 dose, with last dose at Week 12). Eligible subjects will be randomized in a ratio of 2:1 at Baseline to receive subcutaneous injections of nemolizumab (CD14152) (i.e., group 1) or placebo Q4W (i.e., group 2).

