Clinical assessments will occur according to the schedule of assessments through the Week 16. Subjects who are clinical responders at Week 16 will continue to the Maintenance Period. Subjects who discontinue the Initial Period prematurely should complete an Early termination (ET) visit and a Follow-up visit 12 weeks after the last study drug injection. Subjects who are non-responders at Week 16 may be eligible to enroll into the LTE study (Protocol 118163). Subjects who require rescue therapy for clinical worsening of AD before Week 16 may also be considered for LTE study participation but will be required to continue with study visits until the Week 16 visit is due. The Follow-up visit is not required for subjects who participate in the LTE study.

Maintenance Period (Re-Randomization: Week 16 to Week 48):

The Maintenance Period is defined as Week 16 (Maintenance Baseline) to Week 48. All nemolizumab (CD14152)-treated subjects (i.e., group 1) who are clinical responders at Week 16 will be re-randomized (1:1:1) to study medication, as follows: group 1A, nemolizumab (CD14152) 30 mg Q4W; group 1B, nemolizumab (CD14152) 30 mg Q8W; or group 1C, placebo Q4W.

This document is confidential.

[figure not shown]
All placebo-treated subjects (i.e., subjects in group 2 from the Initial Period) who responded to placebo during the Initial Period will continue to receive placebo Q4W in the Maintenance Period. Beginning at Week 16, subjects in group 1A will receive active (i.e., nemolizumab [CD14152]) study drug injections Q4W up to Week 44. Subjects in group 1B will receive active (i.e., nemolizumab [CD14152]) study drug injections Q8W, with placebo at alternating visits to maintain the blind. Group 1B subjects will receive the last active study drug injection at Week 40 (final injection at Week 44 will be placebo). Group 1C subjects will receive placebo Q4W (i.e., through Week 44).

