6.3. Safety Population

The safety population will comprise all subjects in ITT population who receive at least 1 dose of study drug. All safety data will be summarized based on the safety population under the treatment group 'as treated'.

For Maintenance Period, only subjects in ITT population who received at least one drug in the Maintenance Period will be included in the population.

Subject who are treated on error during the course of the study will be assigned to actual treatment as described below.

Initial Period:

- Subjects who are randomized to Placebo but treated at least once with Nemolizumab in error will be assigned to 'Nemolizumab Q4W'.
- Subjects who are randomized to Nemolizumab but treated at least once with Placebo in error will still be assigned to 'Nemolizumab Q4W'. If they always received Placebo in error during the period, then they will be assigned to 'Placebo'.

Maintenance Period:

- Subjects who are re-randomized to Nemolizumab Q4W but treated at least once with Placebo in error will be assigned to 'Nemolizumab Q4W to Q4W'.
- In case of subjects who re-randomized to Nemolizumab Q8W, they are supposed to receive Nemolizumab and Placebo alternately. If they are treated with Nemolizumab instead of Placebo at least once in error, they will be assigned to 'Nemolizumab Q4W to Q4W'. However if they are treated

This document is confidential.

at least once with Placebo instead of Nemolizumab in error will be assigned to 'Nemolizumab Q4W to Q8W'.

- Subjects who are re-randomized to Placebo but treated with Nemolizumab at least once in error will be assigned to 'Nemolizumab Q4W to Q4W'.
- Subjects who are randomized to Placebo for Initial Period and continue the Maintenance Period will be assigned to 'Placebo' even if treated with Nemolizumab at least once in error.

Overall Period:

- If subjects exited the study after Initial Period (i.e., not re-randomized nor continued with Placebo for Maintenance Period), overall period treatment group will be the same with Initial period treatment group assigned (i.e., can be either 'Nemolizumab Q4W' or 'Placebo').
- In case subjects who re-randomized for Maintenance Period,
 - Subjects who are re-randomized to Nemolizumab Q4W will be assigned to 'Nemolizumab Q4W' even if they treated by Placebo in error during the study.

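### The Nemolizumab 30mg Q4W column of the overall-study-period adverse-event tables is a post-randomisation subset set beside an intact placebo arm, and SAP 13.1 and 6.3 do not agree on who belongs in it

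*SAP*

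**What the plan says.** SAP 13.1 plans adverse-event tables for the overall study period, meaning initial, maintenance and follow-up together: "The overall study period summary will be presented by 4 treatment groups". These are Nemolizumab 30mg Q4W, Q4W to Q8W, Q4W to Placebo, and Placebo. The first is defined thus: "Nemolizumab 30mg Q4W includes all subjects in the population who received Nemolizumab 30mg in Initial Period or who received Nemolizumab 30mg Q4W continuously" through both periods. Placebo is defined in parallel terms and covers everyone given placebo in the Initial Period, whether or not they went on.

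SAP 6.3 assigns an overall-period group to each subject. For those who leave after the Initial Period, the "overall period treatment group will be the same with Initial period treatment group assigned". Responders re-randomised to Q4W also go to Nemolizumab Q4W. Responders re-randomised to Q8W or placebo are given their own groups, although those rules are worded around dosing errors, some of which move a subject back to Q4W.

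Under SAP 4.1 re-randomisation applies only to nemolizumab subjects "who are clinical responders at Week 16 will be re-randomized (1:1:1) to study medication"; placebo responders simply continue on placebo.

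The overall-period tables give numbers and percentages of subjects. Exposure-adjusted rates are planned for the Treatment Period only (Tables 14.3.1.4.1 and 14.3.1.5.1). No weighting or interpretive note is given for the overall-period tables. The index in SAP section 19 lists twelve of them: six overall summaries and six by system organ class and preferred term, counting the country and age-group versions.

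**The concern.** Which nemolizumab subjects remain in the Q4W column depends on what happened after randomisation. A subject can leave that column only by responding at Week 16 and then being drawn to Q8W or placebo. Dosing errors aside, no non-responder or dropout leaves it. The Placebo column loses nobody. A reader who compares the two adjacent columns is therefore comparing a subset selected partly on outcome with a complete randomised arm.

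The follow-up behind the percentages also differs. Most subjects in the Q4W column are in treatment for 16 weeks or less, while the two switch columns consist entirely of responders, who can be treated to Week 48. Crude percentages do not allow for this. If responders and the rest differ in adverse-event risk, the column misstates the incidence in the nemolizumab arm even when the drug has no effect on that event.

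**Working it through.** **Inputs.**
- SAP 4.1: "Approximately 750 total subjects will be randomized (2:1) to receive either nemolizumab (CD14152) or placebo", so 500 nemolizumab and 250 placebo. All are taken as dosed.
- Protocol 8.1: "it is estimated that 15% of subjects will drop out from the initial treatment period".
- Protocol 8.1: "Assuming a 45% responder rate with active treatment and 12% with placebo". It expects 216 subjects in maintenance, 190 from nemolizumab and 26 from placebo.
- Re-randomisation 1:1:1; dosing errors ignored.

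**1. Reproduce the protocol's figure.** Responders = N × (1 − dropout) × responder rate.
- Nemolizumab: 500 × 0.85 × 0.45 = 191.25 (stated 190).
- Placebo: 250 × 0.85 × 0.12 = 25.5 (stated 26).
- Total 216.75 (stated 216). The figures agree after rounding; the stated ones are used below.

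**2. Composition of the columns, on the mutually exclusive reading.**
- Responders leaving the Q4W column: 190 × 2/3 = 127. Staying: 190/3 = 63.3.
- Non-responders and dropouts: 500 − 190 = 310.
- Q4W column: 310 + 63.3 = 373.3.
- Non-responder/dropout share of the column: 310/373.3 = 83.0%. Share of the randomised arm: 310/500 = 62.0%. Excess: 21 points.
- Each switch column: about 63 subjects, all responders.
- Placebo column: (250 − 26)/250 = 224/250 = 89.6% non-responders or dropouts, the same as its randomised arm.

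**3. Range.** With responder rates of 45%/12%, or 49%/19% (the EASI-75 assumption in Protocol 10.2), and dropout of 0 or 15%, the share is 76–83% in the Q4W column against 51–62% in the nemolizumab arm. The excess is 21–25 points. Placebo is 81–90%.

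**4. Effect on a crude percentage.** Shift = (column share − arm share) × (risk in non-responders/dropouts − risk in responders). The documents give no such risk difference, so 10 and 20 points are assumed:
- 0.210 × 10 = 2.1 points
- 0.210 × 20 = 4.2 points

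The sign follows the sign of the risk difference.

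**5. Treatment-period time.** Assumed: dropouts (75 nemolizumab, 37.5 placebo) leave at 4 to 12 weeks, other non-responders stop at 16, responders reach 48.
- Q4W column: (75 × 4 + 235 × 16 + 63.3 × 48)/373.3 = 19.0 weeks, rising to 20.6 with dropout at 12 weeks.
- Placebo: 17.5 to 18.7 weeks.
- Whole nemolizumab arm: 26.4 to 27.6 weeks.
- Each switch column: 48 weeks.

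**6. The literal reading of SAP 13.1.** If everyone given nemolizumab in the Initial Period is in the Q4W column, it holds 500. The four columns then hold 500 + 63.3 + 63.3 + 250 = 877 entries for 750 subjects.

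**The case against.** The strongest reply is that SAP 13.1, taken at its word, already puts all 500 nemolizumab subjects in the Q4W column, and that the removal of 127 responders is inferred from SAP 6.3, where the Q8W and placebo rules mainly address dosing errors. The ambiguity is real. But the literal reading makes the second half of the definition redundant, makes the columns overlap and contradicts 6.3. The text needs correcting on either reading.

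Several other replies stand and limit the point:
- SAP 13 and 13.1 also present safety by study period, so the Initial Period summaries keep the randomised comparison. The overall-period display covers only two table types and their subgroup repeats, and no test is planned on it.
- Treatment Period exposure-adjusted rates and the Overall Period exposure summary in SAP 9.6 already address part of the exposure problem.
- A label such as Q4W to Q8W names a sequence, so showing first-16-week events there is not a misattribution. Events after re-randomisation appear in the Maintenance Period summaries.
- In both composition and follow-up time the Q4W column is nearer to placebo than the whole nemolizumab arm is. A whole-arm column widens the time imbalance and, unless this is handled, counts up to 32 weeks on placebo in group 1C as nemolizumab.

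None of these turns the Q4W column back into a randomised arm.

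**Conclusion.** The point holds on the mutually exclusive reading. The Q4W column omits about 127 of 190 expected responders with all their events, is about 83% non-responders or dropouts against 62% in the randomised arm, and stands beside an intact placebo arm. Its crude percentages may differ from those of the randomised nemolizumab arm by about 2 to 4 points under the assumed 10 to 20 point risk difference. The counts rest on the protocol's planning figures, full dosing and no dosing errors.

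Three stronger conclusions that a reader might draw are not supported:
- *The column overstates nemolizumab risk by about a third.* The ratio 500/373.3 = 1.34 applies only if no responder has the event. If only responders have it, evenly across the three re-randomised groups, the ratio is 500/(3 × 373.3) = 0.45. The documents do not settle the direction.
- *The column is enriched for non-responders relative to placebo.* It is not: 83% against about 90%. The enrichment is relative to its own randomised arm.
- *The trial lacks a valid safety comparison.* The Initial Period summaries provide one, and no efficacy result is touched.

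**What to change.** 1. Reconcile SAP 13.1 with 6.3: state that the four overall-period columns are mutually exclusive, and give the assignment of error-free Q8W and placebo switchers outright, not only through the dosing-error rules.
2. Add to the overall-period tables an all-nemolizumab-treated column, everyone dosed with nemolizumab in the Initial Period, beside Placebo. Give exposure-adjusted incidence rates, with events and person-time counted over the same interval. Exclude events and time after re-randomisation to placebo (group 1C), or show them separately.
3. Footnote the four-column display as descriptive and not a randomised comparison.

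The cost is SAP wording, one re-programmed column set reused across the twelve tables, and a written rule for post-switch placebo time. No new data are needed. Restricting the Q8W and placebo-switch columns to events after re-randomisation is unnecessary, because the Maintenance Period summaries already show those events.
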